Participants will be the sole source of data for this study and all data will be obtained specifically and exclusively for research purposes. Data collection will take place during in-person or remote baseline sessions, and remotely via online follow-up surveys. All collected data will be held confidential. Survey software Qualtrics ensures protection of information through its firewall systems and regular scans for vulnerabilities. The confidential system component design restricts access to outside parties and Qualtrics' use of Transport Layer Security (TLS) encryption protects all transmitted data.

12.3. Access to Individually Identifiable Information.

All participants will be assigned a unique ID. These IDs will be used to identify all participants on all research materials, surveys, tracking forms, as well as the database. Participants' names will never appear in any report resulting from the project. Separate from research records, an identifier key will be created that will link the participant ID to subject names and contact information, to facilitate follow-up with participants; contact information will have participant ID numbers but will not have any data. All data will be stored separately from identifying documents (e.g., participant tracking data base with names and phone numbers). Only the PIs and the research assistants will have access to project data until it is de-identified. Electronic data will be secured and accessible only through password protected computers. We will adopt the following measures to safeguard the data and participant confidentiality:

- All staff will be trained in procedures for maintaining confidentiality of participant information
- Electronic data collection forms will be identified by a unique identification number linked to an identifier list;
- The identifier key will be stored separately from the data collection forms and accessible by the only the research staff;
- Data will be stored on our password-protected computers and backed up to a secure server. Access to this server is password protected and only known to the PIs and RAs and backed up daily.
- We recommend that participants respond to follow-up surveys in a private location, and upon completion they close their browser to protect their privacy.
- At the end of the study, all personally identifying information will be erased. The data may be posted online when research results are published but it will not contain any information that could identify an individual or their participation in this research study.

12.4. Programming Technology and Web Security.

Information submitted via web-based surveys at baseline and at the follow-up assessments will be stored in a secure server at Brown University. The technology for transmitting and storing data includes Transport Layer Security (TLS) encryption (also known as HTTPS) and firewalls to protect the data and to prevent unauthorized access. We will download data from the Qualtrics website, and upload it to the secure Brown servers, at the end of each semester. When the study is over, we will ensure that the data are all removed from Qualtrics servers.

The screening survey will be completed anonymously, and screening data are unlinked to contact information obtained in the scheduler, so that we will not know the identities of students who complete the screener. During the RCT, face-to-face contact with participants is limited to the baseline/intervention session; research staff will be trained to identify adverse events (defined below) and report the to the site-specific contact. Similarly, any safety concerns raised by participants through study-related electronic/phone communications will be reported by research staff to the site-contacts, who will be prepared to provide referrals to their respective campus counseling centers. Finally, electronic surveys completed by participants will not be monitored at an individual basis, because of assurances that

responses to questions will not be associated with names, but each will end with a list of counseling centers and alcohol and drug services, as well as the number for a 24-hour crisis hotline. All data will be stored electronically on the secure server at the Brown Center for Alcohol and Addiction Studies. A password will be required to access data that are stored electronically, and only personnel involved with the project will have access to the electronic data.

12.5. Protocol Amendment History

IRB submissions

Project: CAA R01, Using Counter Attitudinal Advocacy to Change Drinking Behavior (R01AA025043)

Year 1 start date: 9/15/18

Year 2 start date: 7/1/19

IRB Submissions

Project: PROJECT RAVEN: Using Counter Attitudinal Advocacy to Change Drinking Behavior

Brown # 1906002478		Date submitted or revised	Date approved
Submission type	Content		
Initial application	Full application for RCT at Brown and UH; Brown IRB leads	6/28/19	
Revisions requested by IRB	
Questions/Requests:
 
 ▪ The application is checked that you have completed GCP training, but I don't see that certification in CITI. If you completed GCP through another institution in the past 3 years, would you forward that certificate to me? If not, would you complete one of Brown's CITI GCP modules? ▪ In the Baseline Survey - Demographics, #18 (Immigration Generation), what is the justification for asking about the immigration status of the participant and their parents? Although written in general terms, this question has the potential to cause discomfort or distress. ▪ The consent document with my comments and track-changed recommended revisions is attached. Please accept the recommendations you like, address the question, and correct the document for any errors caused by the track changes. 
Application Revisions:
 
 ▪ Part III, #3 (Intervention) states that "the oral presentation component of the CAA activity serves (a) to make the statement public." Do you intend to make these presentations publicly available? If so, please confirm that all identifiable information will be redacted before release. 	8/12/2019	8/21/19

	
 ▪ Part III, #5 (Recruitment Methods) states that this study does not involve an intervention, but the study meets the definition of a clinical trial and involves a behavioral intervention. Would you update this section with the applicable information? ▪ Part V, #2 (Facilitating Understanding) states that only English-speaking participants will be enrolled. Considering this is a large clinical trial, what is the justification for excluding non-English speakers? ▪ The checked box in Part VII, #1D is not clear on whether the data meets Level 2 or Level 3 risk. Would you clarify this section? 
Recruitment and Communication Material Revisions:
 
 ▪ In all Brown and UH recruitment material, please remove all references to compensation in titles/headers and language throughout that may cause undue influence (for example, "Help advance" or "Help improve"), as this type of language is not allowable per the HRPP recruitment policy. ▪ In the CAAS Find A Study, please add "research," as it does not specify the recruitment is for a research study. ▪ In the Flyer Text, please remove any language throughout that may cause undue influence (for example, "advance" or "improve"), as this type of language is not allowable per the HRPP recruitment policy. ▪ In the Post on Facebook Class Pages, it says "(If from personal account...)." Will research staff recruit prospective participants from their personal Facebook accounts? If so, what is the rationale behind this, as opposed to creating a Project RAVEN Facebook page? ▪ In the Electronic Communications with Participants, please ensure the e-mails consistently specify the communication is for a "research" study. 		
Amendment 1 submitted by us	
 ▪ To establish an IAA with Houston using Brown as the IRB of Record 	8/12/2019	9/26/2019
Amendment 2 submitted by us	
 ▪ Changed one item on the screener survey ▪ Removed one sentence from consent 	9/27/2019; revision requested and resubmitted on 10/25/19	10/25/2019
Amendment 3 submitted by us	
 ▪ Addition of remote procedures ▪ Remote/Online consent form 	3/13/2020; revision request &	3/17/2020

	
 ▪ Remote recruitment materials (revised appendix A) 	resubmitted on 3/17/2020	

Amendment 6 submitted by us	
 ▪ Sharing deidentified data between Brown and University of Houston using a secure DropBox folder shared only with study personnel directly involved with 	12/18/2020	1/14/2021

	
the project (principal investigators and the project manager at each site)
 
 ▪ Addition of [name] as a research assistant 		
Revisions requested by IRB	
 ▪ Proof of investigator CITI training and request that [name] be added as a COI (Appendix G was sent to display that he was included on the original submission) 		
Amendment 7 submitted by us	
 ▪ Addition of a question to all assessments time points (baseline, 1-, 3-, and 6-month follow ups) asking about COVID vaccination status ▪ Addition of alternate recruitment announcements and language at the Brown site only. 	2/18/2021	3/02/2021
Amendment 8 submitted by us	
 ▪ addition of alternate recruitment announcements to recruit more male participants at the Brown site ▪ Corresponding update to Recruitment Materials (pp. 2-3), which include edits to Today@Brown subject lines ▪ Use of Microsoft OneDrive to store deidentified study data at the Houston site 	4/23/2021	5/6/2021
Administrative Acceptance 1 submitted by us	
 ▪ Request for the substitution of a new contact person at the Brown and Houston sites in the Consent form ▪ Corresponding change in Online Recruitment Materials at the Brown site 	8/11/2021	8/19/2021
Amendment 9 submitted by us	
 ▪ Revised procedures to remove Microsoft TEAMS for remote participation ▪ Corresponding revised HRPP Consent Form for the Houston site 	8/26/2021	9/2/2021

Greetings from Project RAVEN! We recently invited you to participate in Project RAVEN, a confidential, multi-part research study being conducted through the Psychology Department on campus that examines campus health beliefs and behaviors. This is just a reminder to let you know that there is still time to participate in our survey!

Please take our brief, mobile-friendly, online survey to see if you qualify for a study that could earn you up to \$115 in Amazon gift cards.

<<SURVEY LINK>>

Participation is voluntary and your answers will be kept confidential.

For any related questions or concerns, please contact [name] at [contact] or by emailing [contact].

This study was approved by the Institutional Review Board.

Thank you,

[name]. & the UH Project RAVEN Team

**We cannot guarantee the confidentiality of email communication.*

3. UH Confirmation of Registration Email

Subject Line: Project RAVEN Appointment Confirmation

Greetings from the Project RAVEN team,

Thank you for taking part in our study! You are scheduled for an in-lab session on <<TIME/DATE>> in the [name]. Please contact our office at [contact] if you have questions. We look forward to seeing you.

Thank you,

[name] Ph.D. & the UH Project RAVEN team

**We cannot guarantee the confidentiality of email communication.*

Electronic Communications with Participants (Brown)

Drafts of electronic communications with participants.

All study emails will come from the [contact] or [contact] email addresses issued to this project. The following templates were developed for use at Brown and will be adapted for use at UH.

4. Brown Project RAVEN Baseline Email 1:

Subject Line: Project RAVEN Study Appointment

Dear Student,

Thank you for your interest in the Project RAVEN research study! Your on-campus appointment is scheduled for DATE @ TIME in LOCATION. This appointment should take about 75-90 minutes, and your \$25 Amazon e-gift card will be emailed to you upon completion of the appointment. Please remember to bring your student ID. If you have any questions, please feel free to email us at [contact]. We look forward to meeting you!

Best,

Study Staff: [name], BA

Project RAVEN Study

5. Brown Project RAVEN Baseline Email 2 (Reminder):

Subject Line: REMINDER: Project RAVEN Study Appointment

Dear Student,

As a reminder, your research study appointment is tomorrow DATE @ TIME in LOCATION. This appointment should take about 75-90 minutes, and your \$25 Amazon e-gift card will be emailed to you upon completion of the appointment. Please remember to bring your student ID and check in at the front desk in the lobby (if in the School of Public Health location). If you have any questions, please feel free to email us at [contact]. We look forward to meeting you tomorrow!

Best,

Study Staff: [name], BA

Project RAVEN Study

APPENDIX B. Recruitment Materials and Participant Communications at both sites (post-COVID)
UH Registrar Recruitment Email + Follow up emails**1. UH Recruitment Email:**

Subject line: Paid Online Heath Behaviors Study at UH

Dear <<student name>>,

The Psychology Department on campus is inviting University of Houston students to participate in a confidential, multi-part research study called “RAVEN” that examines campus health beliefs and behaviors. This study can be completed remotely and is entirely online!

Please take a brief, 3-minute online survey to see if you qualify for a study that could earn you up to \$115 in Amazon gift cards.

Please visit <<[SURVEY LINK](#)>> to complete this mobile-friendly survey.

Participation is voluntary and your answers will be kept confidential.

For any related questions or concerns, please contact [name] at [contact] or by emailing [contact].

This study was approved by the Institutional Review Board.

Thank you!

[name]. & the UH Project RAVEN Team,

*WE CANNOT GUARANTEE THE CONFIDENTIALITY OF EMAIL COMMUNICATION.

2. UH Reminder Screening Emails

Subject Line: REMINDER: Paid Online Heath Behaviors Study at UH

Dear <<student name>>,

Greetings from Project RAVEN! We recently invited you to participate in Project RAVEN, a confidential, multi-part research study being conducted through the Psychology Department on campus that examines campus health beliefs and behaviors. This is just a reminder to let you know that there is still time to participate in our survey!

Please take our brief, mobile-friendly, online survey to see if you qualify for a study that could earn you up to \$115 in Amazon gift cards.

[<<SURVEY LINK>>](#)

Participation is voluntary and your answers will be kept confidential.

For any related questions or concerns, please contact [name] at [contact] or by emailing [contact].

This study was approved by the Institutional Review Board.

Thank you,

[name]. & the UH Project RAVEN Team

**We cannot guarantee the confidentiality of email communication.*

3. UH Confirmation of Registration Email

Subject Line: Project RAVEN Appointment Confirmation

Greetings from the Project RAVEN team,

Thank you for taking part in our study! You are scheduled for an online session on <<TIME/DATE>> . Please contact our office at [contact] if you have questions. We look forward to seeing you.

Thank you,

[name] Ph.D. & the UH Project RAVEN team

**We cannot guarantee the confidentiality of email communication.*

4. Brown Electronic Communications with Participants

Drafts of electronic communications with participants.

All study emails will come from the [contact] or [contact] email addresses issued to this project. The following templates were developed for use at Brown and will be adapted for use at UH.

5. Brown Project RAVEN Baseline Email 1:

Subject Line: Project RAVEN Study Appointment

Dear Student,

Thank you for your interest in the Project RAVEN research study! Your Zoom appointment is scheduled for DATE @ TIME in LOCATION. This appointment should take about 75-90 minutes, and your \$25 Amazon e-gift card will be emailed to you upon completion of the appointment. Please remember you will need access to a computer with Zoom, a video camera and a quiet space for 90 minutes. Please have your student ID to display. If you have any questions, please feel free to email us at [contact]. We look forward to meeting you!

Best,

Study Staff: [name], BA

Project RAVEN Study

6. Brown Project RAVEN Baseline Email 2 (Reminder):

Subject Line: REMINDER: Project RAVEN Study Appointment

Dear Student,

As a reminder, your Zoom research study appointment is tomorrow at DATE @ TIME. This appointment should take about 75-90 minutes, and your \$25 Amazon e-gift card will be emailed to you upon completion of the appointment. Please remember you will need access to a computer with Zoom, a video camera and a quiet space for 90 minutes. Please have your student ID to display. If you have any questions, please feel free to email us at [contact]. We look forward to meeting you tomorrow!

Best,

Study Staff: [name], BA

Project RAVEN Study

7. Brown Email for participants who do not show up for scheduled baseline session:

Subject Line: Reschedule Project RAVEN Appointment

Dear Student,

We missed you today and are sorry you couldn't make your scheduled Project RAVEN Zoom session. We hope you are still interested in participating! If so, please visit <scheduling link> to re-schedule your research appointment at a time that works better for you. We would still love the opportunity to get your input on these health promotion programs!

If you no longer wish to participate, we understand, but please reply to this email in order to let us know, and we will remove you from our list.

Best,

Study Staff: [name], BA

Project RAVEN Study

APPENDIX C. Intervention scripts (PNF & CAA)**Remote (Zoom) Baseline Sessions Post-COVID Scripts****Remote Baseline Session Protocol**

This protocol is to be used in the circumstance that a participant cannot come into the lab for an in-person baseline session.

[figure not shown]
Pre-Baseline

- a. When a participant schedules a session, create a Zoom meeting using the information in the confirmation email.
 - i. Log into The UH Project RAVEN Zoom account
 - ii. Click “meetings” tab on the left, then “Schedule a new meeting”
 - iii. Topic: “Project RAVEN Research Session”
 - iv. Description: “This appointment should take about 60-90 minutes, and your \$25 Amazon e-gift card will be emailed to you upon completion of the appointment. Please note that to participate in this study remotely you will need internet access, a computer with videoconferencing capabilities and a quiet, private space for 1.5 hours where you feel comfortable discussing your health behaviors with a research assistant. If you do not have access to these resources, please contact us and we will discuss scheduling an in-person session when classes resume in the fall.”
 - v. When: Enter date and time selected on Setmore
 - vi. Duration: 1hr 30 min
 - vii. Meeting ID: Generate Automatically
 - viii. Meeting Password: Check “Require meeting password” and enter their participant ID
 - ix. Video: Host: on; Participant on
 - x. Audio: Telephone and computer audio
 - xi. Meeting Options: Enable join before host
 - xii. Save
- b. Email the participant the Zoom Invitation email template. Include their individualized Zoom link.
- c. 10 minutes prior to their scheduled time, email the participant the Zoom Reminder email template (see below) which should include their individualized zoom link and a link to the Qualtrics baseline survey

Orientation to Session and Consent

[figure not shown]
1. Begin the Zoom meeting and confirm that you and the participant can see and hear each other
2. Ask the participant about their environment. “Okay, before we begin our session, I need to make sure you’re in an appropriate environment for our call. Could you tell me where you are?” “Okay, is this somewhere private where you feel comfortable discussing your health behaviors with me?”
3. Record the participant’s responses in the tracking excel sheet. If the participant is in a public location or a location with too many distractions, ask that they reschedule their appointment for another time when they can arrange for a more private space.
- a. Instruct them to open the survey link included in their confirmation email.

i. What the participant sees:

[figure not shown]

1. Instruct the participant to enter the password 1540 and then click the blue arrow. Ask them to follow along on their screen as you outline the main points from the Consent Form:
 - This consent form describes your rights as a participant and what participation in this study entails
 - The purpose of this study is to compare health promotion activities for college students
 - Participants in this study are asked to answer several questionnaires and then are randomly assigned to 1 of 3 conditions, two of which entail brief activities
 - If you are asked to participate in an activity condition today, the activity will take about 20-30 minutes and will be recorded to ensure that *I am* following the appropriate study procedures
 - This study has been approved by Brown University's Institutional Review Board
 - Your participation is voluntary, you may withdraw at any point without penalty
 - For completing today's session you will receive a \$25 amazon gift card code via email
 - If you complete all parts of the study (Including the follow-up questionnaires) you will receive a total of \$115 in amazon credit
 - Do you have any questions about the study?
2. Once all questions are answered, ask that the participant click "agree" to certify that they understand and agree to participate in the study then
3. Ask them to click the next arrow

i. What the participant sees:

[figure not shown]
1. “We’ll get you started by filling out a set of questionnaires that’ll take about 30-45 minutes. Let’s turn off our cameras while you respond to the survey, but I’ll remain on the call to answer any questions you have. When you reach the end of the survey, let me know and we can go over the next part of the study”
2. Ask them to click the blue arrow and enter their Participant ID (with an 9 representing a remote participant (e.g., 91040) and select RA Identifier [1 = PNF, 2 = CAA, 3 = Control; based on condition]
 - i. What the participant sees:

1. Turn off your camera and have the participant do the same if they like, but leave the Zoom call on in the background while the participant answers baseline in case they have any questions.
2. When the participant informs you that they have completed their session, proceed based on condition:

CAA Condition

1. When the participant reaches the end of the baseline survey and the password page appears, say “Okay, let’s turn our cameras back on and I’ll explain the next part of the study”.
 - i. What the participant sees:

[figure not shown]

1. Explain the CAA activity to the participant:

- Thank them for completing survey, "now we will ask you to do a brief writing activity that reflects student perspectives on campus health and safety issues"

- Choose one of three topics
- At least 15 minutes to write

- Instruct them to type “raven” into the textbox and click the blue arrow.

- I'm going to turn the camera off. Let me know when you're finished writing & we'll discuss it to make sure I understand what you've written”

2. Turn the camera off while the participant does the writing activity

[figure not shown]
3. When the participant tells you that they have completed the writing activity,

“Okay, let’s turn our cameras back on so that we can discuss what you wrote. What do you see on your screen?”

4. If they are not on the password page yet, instruct them to click the blue arrow to proceed. Next ask them to type “houston” in the RA Identifier box and click next.

[figure not shown]
i.

What the participant sees:

5. Remind the participants "I am going to record our discussion to confirm that I am doing my job"
6. Turn recorder on and set it on the desk near the speaker
 - "So which topic did you select?" (TOPIC is piped in at the top of the page)
 - "Okay, what more specifically were you asked to write about?"
 - "So it sounds like the prompt had multiple parts, could you tell me what you wrote about the first one?"
 - "So it sounds like a good reason to avoid problems is..."
 - "Okay, were you asked to write about anything else?" then, "Okay, and what did you say were some ways students could do that?"
 - "Thanks. So, if I follow correctly, your advice to other students would be to... [two personally relevant, effective and feasible strategies]. Do I have that right?"
 - "Great! Now you'll be given the chance to edit or add to what you wrote and then there are a few more questions for you to answer before we conclude today's session. Just let me know when you complete the survey and I'll turn the camera back on to discuss your compensation."

What the participant sees:

[figure not shown]

6. Turn the recorder and your camera off while the participant answers the follow-up survey

PNF Condition

1. When the participant reaches the end of the baseline survey and the password page appears, turn the camera back on and ask that the participant do the same. Explain the PNF activity to the participant
 - i.

What the participant sees:

2. Let them know you will be screen sharing so that you can discuss the feedback together
3. Instruct them to type “raven” in the RA Identifier box and that another tab will open, but not to proceed while you set up the presentation.
4. Open the baseline completion email and click on the link to open the PNF in a new window (it default opens in a new tab). Move this tab to a new window, Share your screen with the participant, then make the presentation full screen. *Note that if you need to refer to the script/protocol you should have a pre-printed version* Confirm they can see your screen and the graph clearly.
5. Remind the participant “I am going to record our discussion to confirm that I am doing my job“
6. Walk the participant through the PNF activity as you would in person. At the end of each slide, ask the participant what questions/thoughts they have and ask them to let you know when they are ready to proceed. “Im going to give you a minute to look over this graph” PAUSE “What questions do you have/does this make sense/thoughts?”
7. Once you finish the PNF activity, inform the participant that they will now have the opportunity to click through the PNF *on their own* screen and then continue on to finish a few more questions. End the screenshare and turn your camera off.
8. Ask them to let you know when they complete the survey and you’ll turn the camera back on to discuss their compensation.
9. While the participant finishes viewing the PNF and completes the post-intervention survey: Save their PNF slides as PDFs and combine the files into one. Do this by right clicking each PNF page and selecting “Print”, then “Save as PDF”. Save as “RAVEN Feedback_ID_page#” on the server.

[figure not shown]
10. Once saved, merge the three PNF PDF pages together in Adobe and add the composite file to the debrief email to send the participant upon completion.

Control Condition

1. When the participant reaches the end of the baseline survey and the password page appears, turn the camera back on and explain that there are just a few more questions for them to answer. Ask them to type “raven” in the RA Identifier box to proceed. Tell them to let you know when they complete the survey and you’ll turn the camera back on to discuss their compensation.

i. What the participant sees:

[figure not shown]
After finishing the questionnaire

Debrief

1. Ask the participant to click the blue arrow and ensure that their screen reads “We thank you for your time spent taking this survey. Your response has been recorded.”

i. What the participant sees:

1. Verbally confirm their preferred email address

“You will be contacted in around 1-,3- and 6-months from now to complete follow-up surveys, for which you will receive \$25, \$30 & \$35 to Amazon, respectively, for completing. These surveys are much shorter than the one you completed today and should take less than 20 minutes. Do you have any questions about the study?”

2. Tell them that you will email them a resource list now that we give to all participants along with our contact information in case they have any questions about the study
3. Thank them for participating in the study and close out the Zoom call
4. Email the participant the debrief email template, the resource list and the PNF PDF if applicable. Bcc the other RA on this communication, as a back up record in case the tracking document glitches.
5. Fill out the “Appt. Notes” column, if applicable (i.e. notable remarks, demeanor, late arrival, suggestions. Record any questions the participant asked and how you responded here, as well as in “Participant Question List and CAA Notes” on the DropBox)
6. Upload and save the recording on the *server* here: (‘Z:\Project Raven\audio files’ on the [name]\$ drive) with the ID, Condition, your initial and the date recorded (e.g. 1000_CAA_AW_11.13.2019)

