7.3.2 Screening for remote baseline sessions (Houston site)

No changes were made to the screening process at the University of Houston, as the majority of students commuted to campus prior to the pandemic.

7.4. Scheduling participants. Participants who meet screening criteria will be invited to schedule an individual in-person session using an online scheduling module (See Appendix A, Recruitment Materials, for details). The scheduling module will direct participants to select a date and time for their session and ask participants to provide their name, phone number and email address for further research study communications. A staff member will call, text, and/or email to confirm the appointment when it is made and will remind students of their appointment time and date one or two days before the scheduled appointment. At the in-person session, participants will provide written informed consent and complete the online baseline assessment

in a private room. Assignment to condition will take place after their baseline assessment; students will be stratified across conditions based on gender, a practice that has ensured baseline equivalence in drinking across conditions in several prior studies of college drinkers.

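### The remote session script has the condition code entered before the baseline survey, while section 7.4 and the script's own consent summary place assignment after it

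*Combined protocol and SAP*

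**What the plan says.** Section 7.4 of the protocol sets the order for the in-person session: "Assignment to condition will take place after their baseline assessment; students will be stratified across conditions based on gender".

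Appendix C holds the script for remote sessions, to be used when a participant cannot attend the lab. It uses the UH Zoom account. Its consent summary gives the same order as section 7.4: "Participants in this study are asked to answer several questionnaires and then are randomly assigned to 1 of 3 conditions".

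Once the participant has agreed, the research assistant (RA) introduces a set of questionnaires lasting 30-45 minutes. The participant is then asked to enter a participant ID "and select RA Identifier [1 = PNF, 2 = CAA, 3 = Control; based on condition". After that, cameras go off and the RA is told to "leave the Zoom call on in the background while the participant answers baseline in case they have any questions".

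The next instruction that concerns the arms is "When the participant informs you that they have completed their session, proceed based on condition". The CAA, PNF and Control branches each then open at a password page.

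**The concern.** A code chosen according to condition can be entered only if the condition is already set. The script therefore implies that allocation exists, and is known to the RA, before baseline is measured. Two other statements in the protocol say the opposite.

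Three things depend on the order.

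- **The baseline measurement.** Under section 10.2, baseline is the first of up to four assessments in the outcome model. The Time x CAA terms are the direct Aim 1 test, and both mediation paths control for baseline outcomes. These values should be collected before anyone in contact with the participant knows the arm.
- **Who counts as randomized.** Under section 7.4, a student who stops during the survey was never assigned. Under the script, that student has an arm and belongs in the denominator.
- **Reporting.** A reader cannot tell from the documents which order was used in remote sessions, so cannot tell at what point a participant became randomized.

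**Working it through.** The point concerns the order of steps, and no arithmetic applies. The check is to set the sequences side by side.

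| Step | Section 7.4 (in person) | Appendix C, consent summary | Appendix C, operating steps |
|---|---|---|---|
| 1 | Consent | Consent | Consent |
| 2 | Baseline survey | Questionnaires | ID and condition code entered |
| 3 | Assignment, stratified by gender | Random assignment | Baseline survey, RA on the call |
| 4 | Arm-specific procedure | Activity in two of three arms | Proceed by condition |

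**Is the order in the last column certain?** The list numbering in the script restarts several times, so it cannot settle this. The content does. The code is entered after the questionnaires have been introduced, and the following instruction turns the cameras off while baseline is answered. The code step therefore comes before the survey.

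**Is there a later assignment step?** None appears between the end of the survey and the three branches. At the password page the CAA participant types a keyword "into the textbox and click the blue arrow". The PNF participant is told to type it "in the RA Identifier box and that another tab will open, but not to proceed while you set up the presentation". The Control participant types it "in the RA Identifier box to proceed". The keyword is the same word in all three arms, so it cannot be what separates them. In the text supplied, the code entered before baseline is the only recorded item that does.

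**Does any other text change the order for remote sessions?** Sections 7.6.2 and 7.6.4 list the remote changes as consent by Zoom, delivery by Zoom and emailed materials, with the end of phone reminders at UH. Neither mentions the timing of assignment. The amendment history in section 12.5 records that remote procedures were added, without detail on this point.

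**Result.** The operating steps cannot both be followed and agree with section 7.4 or with the consent summary.

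**The case against.** The strongest reply is that this is a mismatch of wording. The consent summary is a lay account of the session as the participant experiences it, and section 7.4 speaks of the in-person visit. The arm might have been drawn in advance and merely delivered after baseline. The script uses the RA Identifier label loosely, for arm codes in one place and for keywords in others, and the screenshots are missing. Some of the amendment history is also not available, and the lists in section 7.6 are headed as participant communications, so their silence proves little.

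Part of this stands. The available text cannot show that no reconciliation exists anywhere, and the consent summary is weaker evidence than an operating instruction. But advance allocation delivered later is still not assignment after baseline, and the RA would still hold the arm during the survey. The bracketed codes name the three arms, so loose use of the label does not remove the difficulty.

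A reader might go further in four ways that the documents do not support.

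- *That baseline data are biased.* The code follows consent, and baseline is a self-completed web survey with the RA's camera off and the RA available only for questions.
- *That participants knew their arm.* The screens are not shown, so it is unknown whether the options carried arm names.
- *That the UH target of 300 caps the affected sessions.* UH ran in-person sessions until 5 March 2020, which points to fewer. Brown moved to remote sessions too, and whether it used this script is unknown, which could mean more.
- *That gender stratification failed.* Section 12.4 says screener answers are unlinked to scheduling contacts, and section 9.1.1 collects gender at baseline. How gender was known at code entry is therefore unexplained, but that does not show a failure.

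**Conclusion.** The concern holds as an inconsistency in the documents that should be corrected. As written, the remote script produces an allocation order that section 7.4 and the script's own consent summary say is not used. Following it means that the RA knows the arm throughout the 30-45 minute baseline survey, and that students who leave during the survey have already been allocated.

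The size of any effect cannot be determined, because the documents give neither the number of sessions run from this script nor the number of withdrawals during the survey. The conclusion rests on reading the script literally and on the text supplied. It would reduce to a script error if practice in remote sessions in fact followed section 7.4.

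**What to change.** Amend the remote script in Appendix C so that only the participant ID is entered before baseline. Draw, reveal and enter the condition at the password page that already ends baseline in every arm, using the gender recorded in that survey for the stratified draw. Extend section 7.4 to say that the same order applies to remote sessions, who or what generates the allocation, and whether Brown used this script.

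For sessions already run with the code entered first, count everyone who was given a code as randomized and report withdrawals after code entry by arm. Disposition is already a heading in the twice-yearly report to the monitoring board (Appendix E, Communication Plan), so no new reporting route is needed. If practice followed section 7.4, correcting the script and saying so is enough.

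The cost is modest but is more than moving a field. Gender must reach the RA, or a randomizer inside the survey, as soon as baseline is finished, and the branch into the three arms must be triggered at that page. The PNF branch already relies on baseline answers at that moment, since the feedback is built from them and the RA opens it from a baseline completion email. The documents do not give the programming effort or say whether that email contains gender.
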